## C. Summary of Serious Adverse Events:

All serious adverse events that occur during the course of the study will be indicated on the adverse event record. A listing should be provided with treatment group. This will include serious adverse events that are considered either related or unrelated to the study device.

Patient narrative summaries will be provided for each report.

## D. Special Topics-Headache, Pain/Discomfort:

After summary of the overall adverse event reports is complete, inspection of these adverse event terms will be performed and selected term grouped for the two key domains of headache and pain/discomfort near the treatment location will be clustered. These group terms will be summarized in terms of their incidence across the time points of observation in Phase I to determine whether or not there is severity and time course of accommodation to these effects.

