Repositioning of coil, consistent with the guidelines in the NeuroStar User Manual, and prophylactic use of acetaminophen or ibuprofen will be allowed for subjects reporting sensations at or near the stimulation site which are uncomfortable or painful. During the first week of treatment only, in the event that the participant cannot tolerate the treatment at the stipulated study dose parameters, dose intensity may be titrated downward to 110% of the motor threshold, with all other dose parameters remaining the same.

Treatment plan for other potential side effects experienced *following* treatment:

Subjects reporting headaches during or following study treatment will be encouraged to take acetaminophen or ibuprofen prior to the daily treatment. To reduce the risk of temporary or permanent hearing loss due to noise emitted from the stimulator, subjects will wear protective ear plugs during treatment. All subjects will be monitored, and appropriate treatment will be recommended including the possibility of stopping TMS. Any other potential side effects will be managed symptomatically with treatment(s) deemed appropriate by the study site Principal Investigator. All symptomatic interventions will be recorded in the subject's case file and, if applicable, adverse event CRF.

Treatment with the Neurostar TMS Therapy System may involve other risks that are not known at the present time. The long-term effects of TMS are not known.

Page 23 of 61

Structural Head MRI

As this study only involves up to four MR scans (Phase I Baseline; End of Phase I/Phase II Baseline; End of Phase II; End of Phase III [LTFU]), the risk is assessed as minimal. No contrast material or exposure to ionizing radiation will occur for the conduct of this protocol.

To minimize any potential risks from the scans, the physician will ensure that the subject does not meet any contradictions for an MRI. Subjects who are uncomfortable in enclosed places (claustrophobic) may experience some discomfort. The MRI staff will be in contact with subjects at all times throughout the scanning process, and if necessary the scan can be stopped at any time. The total scanning time will be approximately 30 minutes per scanning session.

Overall Risk Analysis Statement

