10.2 Efficacy and Safety Assessments

Phase I

See Appendix A for schedule of events.

Outcome Assessments

Trained physicians and raters will administer all diagnostic assessments and clinical interviews determining study eligibility during screening and prior to randomization. All study staff will be trained on study procedures by Neuronetics staff.

Outcome screening will occur after both the Informed Assent/Consent Document and the HIPAA Authorization are signed. Baseline assessments will occur prior to the first TMS treatment session. Outcome measures in Phase I will be assessed at the end of treatment weeks 4 and 6. The following outcome assessments will be completed: HAMD/MADRS structured interview, CDRS-R, CGI-S, and QIDS-A17-SR.

Safety Assessments

A physical and complete medical and psychiatric history will be obtained at the screening visit.

Page 26 of 61

Vital signs including height, weight, blood pressure and heart rate will be collected at the baseline visit and at week 6.

Laboratory determination will be measured at screening and include: Blood chemistry, hematology, urine drug screen, and urine pregnancy for female subjects.

Subjects will be evaluated clinically for adverse events at each visit. Serious adverse events (SAEs) will be recorded as they occur and reported to Neuronetics by the study site within one business day of notification.

Cognitive function assessments will be conducted at the baseline visit and at week 6. The following tests from the NIH Toolbox Cognition Battery are used for this study:

- Education
- Handedness
- Attention
 - o Flanker Inhibitory Control and Attention Test
- Episodic Memory
 - Picture Sequence Memory Test
 - Auditory Verbal Learning Test (Rey)
- Executive Function
 - Dimensional Change Card Sort Test
 - Flanker Inhibitory Control and Attention Test
- Language
 - Picture Vocabulary Test
 - Oral Reading Recognition Test
- Processing Speed
 - Pattern Comparison Processing Speed Test
- Memory
 - List Sorting Working Memory Test

The C-SSRS will be completed weekly during TMS treatment to assess worsening of illness and suicidality. The YMRS will be completed at baseline and will be repeated based on reported change in symptoms.

Air conduction thresholds will be assessed for both left and right ears at the baseline visit and at week 6.

Phase II

See Appendix B for schedule of events. The schedule of efficacy and safety measures for Phase II will be identical to that of Phase I.

Phase III

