16.4 Reporting Procedures

At each required study visit, all AEs that have occurred since the previous visit will be recorded in the adverse event record of the subject's CRF. The information recorded should be based on the signs or

Page 45 of 61

symptoms detected during the physical examination and clinical evaluation of the subject. In addition to the information obtained from those sources, the subject should be asked the following nonspecific question: "How have you been feeling since your last visit?" Signs and symptoms should be recorded using standard medical terminology.

The following AE information must be included (when applicable): the specific condition or event and direction of change; whether the condition was preexisting (i.e., an acute condition present at the start of the study or history of a chronic condition) and, if so, whether it has worsened (e.g., in severity and/or frequency); the dates and times of occurrence; severity; causal relationship to the investigational device; action taken; and outcome.

Causal relationship options and definitions are as follows:

- *Definitely related*: Event can be fully attributable to administration of the investigational device.
- *Probably related*: Event is most likely to be explained by administration of the investigational device, rather than the subject's clinical state or other agents/therapies.
- *Possibly related*: Event is as likely explained by administration of the investigational device, as by the subject's clinical state or other agents/therapies.
- *Probably not related*: Event is most likely to be explained by the subject's clinical state or other agents/therapies, rather than the investigational device.
- *Definitely not related*: Event can be fully explained by the subject's clinical state or other agents/therapies, rather than the investigational device.

When assessing the relationship between an investigational product/protocol and an AE, the following parameters are considered:

- Temporal relationship between the investigational device/protocol and the AE
- Biologic plausibility of relationship
- Subjects' underlying clinical state or concomitant agents/therapies
- Where applicable, whether the AE abates on discontinuation of the investigational device (dechallenge)
- Where applicable, whether the AE reappears on repeat exposure to the investigational device (rechallenge)

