## **B.** Adverse Event Reporting:

The general methodology for adverse event collection is discussed in the study protocol. All verbatim reported adverse events are coded using the current version of the Medical Dictionary for Regulatory Activities (MedDRA). All adverse events are categorized by the investigative site staff by severity (3-tier) and by relatedness to the study device (5-tier).

Protocol-emergent adverse events will be reported separately for the Phase I, Phase II, the taper phase, and Phase III. For each study phase, tabular display of adverse events should be provided as follows:

- 1) Adverse events by system organ class and preferred term
- 2) Adverse events by system organ class, preferred term and severity
- 3) Adverse events by system organ class, preferred term and relationship to study device.

44-02219-204, Rev C 21-JAN-2019

Page 21 of 28

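### SAP 8.D judges accommodation to headache and site pain from an undefined incidence; counted as new onsets, it is expected to decline over the weeks even if no patient accommodates

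*SAP*

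**What the plan says.** SAP Section 8.D clusters selected adverse event terms into two domains, headache and pain or discomfort near the treatment location. It then summarises the grouped terms by their "incidence across the time points of observation in Phase I to determine whether or not there is severity and time course of accommodation". It gives no definition of incidence, no denominator, no comparison with sham and no treatment of events that continue or recur.

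The data come from routine adverse event collection. Protocol 10.2 says "Subjects will be evaluated clinically for adverse events at each visit". Protocol 16.4 says that at each required visit "all AEs that have occurred since the previous visit will be recorded in the adverse event record", and lists among the items to capture "the dates and times of occurrence; severity; causal relationship to the investigational device; action taken; and outcome". Protocol 16.3 has events followed until they subside. An end date is not named explicitly, and no rule says whether a recurring pain is one record or several.

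Protocol 8.4 bears on the time course: "Subjects reporting headaches during or following study treatment will be encouraged to take acetaminophen or ibuprofen prior to the daily treatment". The same section permits prophylactic analgesics for site discomfort. Protocol 8.4 and 13.1 allow a lower intensity in the first week only, and 13.1 aims to return to the maximum by the end of that week.

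**The concern.** Accommodation is a change within affected patients: someone who hurts in week 1 hurts less, or not at all, as sessions continue. A count of new onsets does not measure that. A patient whose site pain begins in week 1 and continues unchanged to week 6 adds one event to week 1 and none later. As susceptible patients have their first report, fewer remain to be counted, and the curve falls whatever happens to the pain.

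Safety is part of the primary objective in Protocol 9.1. Application site pain has the highest active-arm rate in Protocol Table 1, at 35.8% against 3.8% on sham in adults. SAP 8.D is the only by-time analysis of these events in the plan. A statement that adolescents adapt to treatment could therefore rest on a counting convention that nobody has chosen in advance.

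**Working it through.** SAP 8.D states no figure, so there is nothing to reproduce. The check asks what weekly counts to expect when there is no accommodation.

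**Inputs from the documents**
- 50 active patients (Protocol, Study Summary).
- 30 sessions in 6 weeks, so 5 per week (Protocol 10.1).
- Adult application site pain on active treatment: 59/165 = 35.8% (Protocol Table 1).

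**Assumptions**
- The adult rate stands in for adolescents and for site pain only.
- The chance *p* of pain per session in a susceptible patient is constant over time. This is what no accommodation means here. No value is given in the documents, so a range is shown.
- There is no dropout, and no effect of analgesics or intensity changes.

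**Pain concentrated in a susceptible share *s* = 0.358**

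New onsets in week *k*, as a share of all treated: s × (1 − p)^(5(k−1)) × [1 − (1 − p)^5].

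Patients affected in any week: s × [1 − (1 − p)^5], the same for every *k*.

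At p = 0.3, 0.7^5 = 0.168. Week 1 is 0.358 × 0.832 = 29.8%, week 2 is 29.8% × 0.168 = 5.0%, and week 3 is 5.0% × 0.168 = 0.8%.

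At p = 0.1, 0.9^5 = 0.590. Week 1 is 0.358 × 0.410 = 14.7%, and each later week is 0.590 times the one before.

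**One low risk shared by all patients**

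Setting the six-week cumulative rate to 35.8% gives p = 1 − (1 − 0.358)^(1/30) = 0.0146, or 7.1% per week. New onsets are 50 × 0.071 = 3.6 patients in week 1 and 3.6 × 0.929^5 = 2.5 in week 6.

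| Scenario, no accommodation | New onsets, weeks 1 to 6 (%) | Affected each week (%) |
|---|---|---|
| Susceptible share, p = 0.3 | 29.8, 5.0, 0.8, 0.1, 0.0, 0.0 | 29.8 throughout |
| Susceptible share, p = 0.1 | 14.7, 8.7, 5.1, 3.0, 1.8, 1.1 | 14.7 throughout |
| Susceptible share, p = 0.05 | 8.1, 6.3, 4.8, 3.8, 2.9, 2.2 | 8.1 throughout |
| Shared risk, p = 0.0146 | 7.1, 6.6, 6.1, 5.7, 5.3, 4.9 | 7.1 throughout |

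**How often a single trial would look this way**

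In 20,000 simulated trials per scenario, new onsets in week 1 exceeded the mean of weeks 2 to 6 in 100% of trials for p of 0.2 or more, in 98.5% at p = 0.1 (susceptible share raised to 0.373 to hold the cumulative rate at 35.8%), and in 59% under the shared low risk. In a separate simulation of 4,000 trials, week 1 was the highest week in 41% at p = 0.05. When affected patients were counted instead, week 1 exceeded the later mean in 46% to 55% of trials, about chance, and never at p = 1.0, where the curve is exactly flat.

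**The missing denominator also matters.** Dividing by patients not yet affected would flatten the shared-risk case at 7.1%. It would not rescue the concentrated case: at p = 0.3, week 2 becomes 5.0/(100 − 29.8) = 7.1%, against 29.8% in week 1.

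**The case against.** The strongest reply is that SAP 8.D never says first onset. Incidence across time points could mean the proportion of patients with the event at each time point, and that count is flat under no accommodation. Protocol 16.4 can be read the same way: a headache on Monday and another on Thursday have each occurred since an earlier visit, so both might be entered with their own dates. This stands. The recording text, together with follow-up to resolution in 16.3, leans toward one record per event, but it does not settle the matter.

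A reader might go further and infer that the plan contains a rule that will nearly always declare accommodation. The documents do not support that. SAP 8.D has no threshold, test or decision, so the simulated percentages are not the error rate of any planned procedure. Even with first-onset counting, a strong early peak depends on pain being concentrated in patients who feel it fairly often. It weakens at low or evenly spread risk, and the per-session risk is unknown.

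Other limits also stand. Headache was not modelled: Protocol 8.4 gives no rate and says only that it was equal in both arms in the adult trial. The unmodelled influences do not all act in one direction. Analgesic use and the loss of intolerant patients would lower later counts, while the return toward full intensity by the end of week 1 could raise them.

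Parts of the remedy exist elsewhere: reasons for discontinuation (SAP 5.B), severity tables (SAP 8.B) and NSAID use by group (SAP 9.A). None is by treatment week, so none supplies the time course that 8.D sets out to describe.

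**Conclusion.** The point holds as a defect of definition. The measure named in SAP 8.D is undefined, and its ordinary reading is biased toward accommodation. Under that reading every scenario examined shows an expected decline with no accommodation. The decline is steep when pain is concentrated in susceptible patients and mild, about 31% from week 1 to week 6 (1 − 2.46/3.55), when a low risk is shared by all. Under the other reading this bias is absent, so an unstated convention would decide what is reported.

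The size rests on an adult rate for one site-pain term and on assumed, constant per-session risks. The section is a descriptive safety summary and feeds no efficacy criterion, so this is an inexpensive improvement and not a threat to the trial's main conclusion.

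**What to change.** In SAP 8.D, replace the undefined incidence with a weekly prevalence table:

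- By arm and treatment week, the proportion of subjects treated that week who have a new or ongoing headache or site-pain event, from event start and stop dates, split by worst severity.
- Describe accommodation from the active-minus-sham weekly prevalence, and from change in severity or resolution among affected subjects who continue treatment. The sham contrast is needed because headache was equal across arms in the adult trial.
- Beside it, show the number who stopped because of these events, analgesic use that week, and week-1 intensity reductions. Prevalence among those still treated is itself affected by dropout and analgesics, and these columns let the reader see that.
- Keep first-onset incidence as a separate, labelled line with its denominator stated.

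The cost is SAP wording and one table, largely from data the protocol already collects. The small downside is its dependence on complete stop dates. Protocol 16.4 does not name these explicitly, so their presence on the case report form should be confirmed, together with whether a recurring event is re-entered.

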## E. Columbia Suicide Severity Rating Scale:

The Columbia Suicide Severity Rating Scale (C-SSRS) will be used in this study to measure the occurrence of suicidal events and behavior. Assessments are completed prior to baseline, each week during active treatment, and at end of phase.

1) Number of Patients with Suicidal Ideation, Suicidal Behavior, and Self-Injurious Behavior with Suicidal Intent (following the format of Table 1 described in the C-SSRS Rating Guide)

Note: This table will report the proportions of patients between active and sham conditions who report positive response on the suicidal ideation items (1-5), the suicidal behavior items (6-10) by item.

2) Table: Shift Table to Demonstrate Changes in C-SSRS Categories from Baseline During Treatment (following the format of Table 3 of the C-SSRS Rating Guide)

Note: This table will report the proportion of patients between active and sham conditions who report positive response on the suicidal ideation items (1-5), the suicidal behavior items (6-10)

#### F. Vital Signs:

Vitals were completed before baseline and at the end of each phase. Changes in Height, Weight and Vitals will be provided.

## G. Cognitive Function Testing:

Cognitive testing will be conducted using the NIH Toolbox. All sites are provided with the NIH Toolbox recommended computer set-up, and are trained on the specific procedures for implementation of the measures to be use in this study. Specifically, eight tests contained within the NIH Toolbox Cognition domain are being obtained in subjects at up to 4 time points in the study (please see the Schedule of Events elsewhere in this document for the specified time points of NIH Toolbox administration).

44-02219-204, Rev C 21-JAN-2019

Page 22 of 28

Data output from the NIH Toolbox are summarized for each test in Table 4 above, and includes Computed Score or Raw Score, Age-Adjusted Scale Score, Fully-Adjusted Scale Score, and Age-Adjusted National Percentile. Data output is extracted from the NIH Toolbox website.

Cognitive Function values are measured at baseline prior to treatment, at the end of each phase, and include the measures listed in Table 4. During the study, the test was moved from a desktop version to an IPAD tablet based version. There were slight changes in the test but both versions contained the same test battery elements.

|--|

Variable Name	Туре	Items
Episodic Memory	- 190	
Auditory Verbal Learning Test (Rey)	Continuous	Raw Score
	~ .	Mean, SD, Median, Range
Picture Sequence Memory Test	Continuous	Computed Score(Age-Adjusted Scale Score) Fully-Adjusted Scale Score
		Age-Adjusted National Percentile
		Mean, SD
		Median, Range
Working Memory	a i	
List Sorting Working Memory Test	Continuous	Raw Score (Age-Adjusted Scale Score), Fully-Adjusted Scale Score
		Age-Adjusted National Percentile
		Mean, SD,
		Median, Range
Executive Function Dimensional Change Card Sort Test	Continuous	Computed Score(Age-Adjusted Scale Score)
Dimensional Change Card Soft Test	Continuous	Fully-Adjusted Scale Score
		Age-Adjusted National Percentile
		Mean, SD
Flanker Inhibitory Control and	Continuous	Median, Range Computed Score(Age-Adjusted Scale Score)
Attention Test	Continuous	Fully-Adjusted Scale Score
		Age-Adjusted National Percentile
		Mean, SD
		Median, Range
Processing Speed Pattern Comparison Processing	Continuous	Raw Score (Age-Adjusted Scale Score),
Speed Test	Continuous	Fully-Adjusted Scale Score
1		Age-Adjusted National Percentile
		Mean, SD,
Language		Median, Range
Oral Reading Recognition Test	Continuous	Computed Score(Age-Adjusted Scale Score)
		Fully-Adjusted Scale Score
		Age-Adjusted National Percentile
		Mean, SD
Picture Vocabulary Test	Continuous	Median, Range Computed Score(Age-Adjusted Scale Score)
Tiotare vocabulary rest	Continuous	Fully-Adjusted Scale Score
		Age-Adjusted National Percentile
		Mean, SD
		Median, Range

## H. Young Mania Rating Scale:

The Young Mania Rating Scale is assessed in all subjects prior to baseline. Upon any indication of activation, mania or hypomania, the scale is repeated during any phase. Descriptive data analysis will be completed for changes reported.

## I. Magnetic Resonance Imaging Substudy:

The MRI substudy was conducted at a subset of sites and was collected before first treatment, and at the end of each phase. The purpose of this study is to evaluate the acute and long-term safety of daily, active TMS in adolescents meeting criteria for Major Depressive Disorder (MDD), single or recurrent episode, as determined by clinical assessment of brain structural integrity using magnetic resonance imaging (MRI) of the head. Clinical assessment will be performed by blinded neuroradiologist reading of patient scans and clinical assessment by standard reading of each scan as normal or abnormal. Analysis will be descriptive.

## J. Auditory Threshold Testing:

Air conduction auditory threshold is obtained at baseline, and repeated up to 3 additional time points in the study depending upon the subject's participation in the various study phases (see Schedule of Events above). Air conduction threshold results are reported as means of right and left dB readings for each of the 8 specified test frequencies across the baseline and end of study phase time points, and the change in dB readings from baseline at the end of study phase time points, using a standard audiogram format and summarizing by study group.

For each of the 8 specified test frequencies both the observed outcome and the change from baseline to end of study phase will be summarized (using the standard audiogram format as noted above). The treatment groups will be compared with respect to the baseline outcome and the change from baseline to end of study phase. The null hypothesis of the equality of the treatment group means will be tested using a t-test. Within each treatment group the statistical significance of the mean change from baseline to end of study phase will be assessed using a paired t-test. For each treatment group the data will be summarized showing the sample size, mean, median, standard deviation, minimum, and maximum.

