	coil operates with an acoustically matched profile that renders the auditory experience of the treatments virtually indistinguishable to subjects or researchers. The sham coil also creates a mild percussive sensation that may be felt by the subject and further assists in simulating the active condition. The blinded randomization of patients in the Phase I acute phase to the active or sham condition will remain blinded for the duration of all study phases including Phases II and III.
Permitted: Zaleplon, zolpidem, or zopiclone (1 dose nightly) as need treatment emergent insomnia or lorazepam (up to 2 mg daily) for tr emergent anxiety, may be administered for up to 14 doses during Pl additional 14 doses during Phase II. For Phase III, these medication administered for up to 10 days, on ≤5 occasions. The use of alternation or anxiolytic compounds requires prior approval from the Sponsor. contraceptives are allowed if the subject has been on a stable dose for months. The use of alternative hypnotics or anxiolytic compounds requires prior approval from the Sponsor. Short-term treatments for headaches, a colds, or flu-like symptoms require prior approval from the Sponsor.	
	Prohibited: Any medication administered for the treatment of any psychiatric or neurologic disorder or any other known CNS-active drugs, including herbal, over-the-counter, and homeopathic medications, MAOIs, other antidepressants, antipsychotics, stimulants and mood stabilizers.

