Motor Threshold Determination ^k							
TMS Retreatment ^{,c,,e,l} (5x/week for 6 weeks)							
See protocol text for description of retreatment parameters							

a. An Informed Consent/Assent for this study must be signed prior to initiating any study-related procedures.

b. Subjects who prematurely discontinue should complete all Month 6 procedures within 2 days after their last TMS treatment session.

c. TMS retreatments should begin on a Monday, with daily treatment sessions occurring on Monday through Friday of each week. All efficacy and safety assessments must be completed prior to the start of retreatment. Efficacy assessments must be completed every other week during each TMS retreatment with the assessment beings conducted after the last treatment for the two week block. TMS treatment to stop when the CGI-S value returns to the Phase III entry score or a full 6 weeks of TMS treatment has been completed. A 3 week taper should follow each retreatment session. TMS retreatment can occur multiple times if symptom re-emergence occurs.

- d. Y-MRS to be completed if symptom indicating mania occurs. If positive, a M.I.N.I./M.I.N.I. KID must be repeated to determine if subject meets full DSM-5 criteria for mania or hypomania. If positive, subject to be discontinued from the study and followed clinically.
- e. C-SSRS to be performed after last TMS retreatment session on last day of the retreatment week.
- f. Performed on a subset of subjects at participating sites.
- g. Audiometry assessments must be performed immediately prior to the start of the TMS retreatment and at the completion of the retreatment course.
- h. Efficacy assessments to be performed the end of each month for monthly visits. Subjects will be called to assess safety and well-being between visits at approximately 2 weeks post previous months visit.
- i. Those AEs occurring following informed consent signature through 30 days after the last study visit will be collected.
- j. Medication treatment for emergent insomnia and emergent anxiety is permitted (refer to protocol for usage allowance).
- k. A Motor Threshold Determination (MT) is to be performed prior to the administration of the first TMS treatment in each treatment course. In addition, motor threshold may be repeated at any time during the course of the active TMS treatment sessions based on clinical assessment of the supervising physician.

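### The hearing analysis in SAP 8.J stays at group level: it plans no count of patients with a threshold shift, its active-sham test cannot see noise common to both coils, and it leaves out the retreatment audiograms

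*SAP*

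**What the plan says.** Protocol Section 8.4 describes the coil's clicking as a possible cause of temporary threshold increases and requires ear plugs to reduce the risk of temporary or permanent hearing loss. Both ears are measured. Section 10.2 states: "Air conduction thresholds will be assessed for both left and right ears at the baseline visit and at week 6". Phase III adds a further requirement, in Appendix C footnote g: "Audiometry assessments must be performed immediately prior to the start of the TMS retreatment and at the completion of the retreatment course".

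SAP Section 8.J sets the analysis. Results are "Air conduction threshold results are reported as means of right and left dB readings for each of the 8 specified test frequencies", displayed "using a standard audiogram format and summarizing by study group". The arms are compared: "The null hypothesis of the equality of the treatment group means will be tested using a t-test". A paired t-test then assesses "Within each treatment group the statistical significance of the mean change from baseline to end of study phase". Each group's data are "summarized showing the sample size, mean, median, standard deviation, minimum, and maximum". The analysis time points are baseline and as many as three later occasions, all tied to the end of a study phase.

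On the sham, the Protocol's Study Summary says that the "coil operates with an acoustically matched profile that renders the auditory experience of the treatments virtually indistinguishable" to subjects and researchers. Sections 8.2 and 12.1 also describe it as acoustically matched.

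**The concern.** Acute and long-term safety in adolescents is a stated secondary objective. The hearing analysis falls short of the risk that the Protocol names in three respects.

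- **No patient-level result.** If only a few patients are affected, group means and t-tests barely move. Nothing in 8.J would say how many patients had a shift, which ones, in which ear, or whether it persisted. Other safety measures in the same SAP do have a patient-level result: C-SSRS counts and a shift table (8.E), and each MRI scan read as normal or abnormal (8.I).
- **A contrast that removes the exposure of interest.** If both coils make the same noise, a noise-related shift occurs in both arms and cancels in the active-sham difference. The SAP does not warn against reading a null difference as reassurance.
- **Data collected without an analysis.** SAP Section 3.A allows up to 72 further treatments in Phase III. The audiograms before and after each retreatment block are the ones closest to that added exposure, yet 8.J analyses phase ends only.

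**Working it through.** 8.J gives no power, SD or criterion, so there is no figure of the plan's own to reproduce. What follows illustrates sensitivity.

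**Inputs from the documents:** 50 patients per arm (Protocol Section 7); two-sided 5% level (SAP Section 2.B, a general statement not repeated in 8.J); 8 frequencies and 2 ears, so 16 readings per patient.

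**Assumptions:** SD of change per ear 3, 5 or 8 dB; a 20 dB shift in one ear at one shared frequency in 3 of 50 patients in each arm; correlation of 0.5 between ears.

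**Step 1, mean shift.** Ears separate: 3 × 20 / 50 = 1.2 dB. Ears averaged: 3 × 10 / 50 = 0.6 dB.

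**Step 2, paired test in one arm, SD 5.** The affected patients also inflate the estimated SD:
- Added variance: (3 × 18.8² + 47 × 1.2²) / 49 = 1128 / 49 = 23.0.
- Estimated SD: √(25 + 23.0) = 6.93. Estimated SE: 6.93 / √50 = 0.98.
- Mean needed for significance: 2.01 × 0.98 = 1.97 dB.
- Sampling SD of the mean with three affected patients fixed: 5 / √50 = 0.707.
- Probability of significance: Φ((1.2 − 1.97) / 0.707) = Φ(−1.09) ≈ 14%. Simulation gives 15%.

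**Step 3, active-sham test, both arms affected, SD 5.** The expected difference is 0. The difference needed is 1.98 × 6.93 × √(2/50) = 2.74 dB, against a sampling SD of 5 × √(2/50) = 1.0. The two-sided probability is about 0.6%; simulation gives 0.7%.

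**Step 4, both arms combined, SD 5.** With n = 100 and 6 affected, the estimated SD is √(25 + 2256/99) = 6.91. The mean needed is 1.984 × 0.691 = 1.37 dB and the sampling SD is 0.5. Φ((1.2 − 1.37) / 0.5) = Φ(−0.34) ≈ 37%.

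Simulated probability of significance:

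| SD (dB) | Paired, ears separate | Paired, ears averaged | Active-sham, ears separate | Arms combined, ears separate |
|---|---|---|---|---|
| 3 | 18% | 14% | under 0.1% | 61% |
| 5 | 15% | 10% | 0.7% | 37% |
| 8 | 11% | 7% | 2% | 21% |

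**Step 5, the planned maximum, SD 5.** With ears separate, the median maximum change is about 24 dB in an affected arm and 11 dB in an unaffected one. With ears averaged it is about 13.7 against 9.5 dB.

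**Step 6, false flags from a per-patient rule.** For a cut-off c applied to any of 16 readings, taken as independent, p = 1 − Φ(c/SD) and the share of unaffected patients flagged is 1 − (1 − p)^16. For c = 10 dB:
- SD 3: p = 0.0004, flagged 0.7%.
- SD 5: p = 0.0228, flagged 31%.
- SD 8: p = 0.1056, flagged 83%.

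Correlation among readings would lower these shares. At the other extreme, with c = 20 dB, a true 20 dB shift is flagged at that frequency only about half the time. The cut-off therefore has to be chosen against test-retest variability.

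**The case against.** A reader might infer that hearing is judged on means alone, so that a loss in a few patients could not show. The documents do not support that. 8.J also plans the minimum and maximum, and with ears kept separate the maximum would usually stand out (Step 5). It would not give the number of patients or identify them.

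A reader might also infer that the acoustically matched sham hides any noise effect. It hides it only in the between-arm test. The within-arm paired tests do not use sham, and at SD 5 dB they have 80% power for a mean change of 5 / √50 × (1.96 + 0.84) = 2.0 dB. They are weak when few patients are affected, but adequate for a broad shift. Nor does the SAP say that a null active-sham result will be taken as proof of safety. Acoustic matching is described by how the coils sound; no dB output is given for either.

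Averaging of the two ears is a possible reading of 8.J, not a stated method. A standard audiogram format can equally mean one mean per ear.

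Other points have weight. The adverse event definition (Protocol 16.1) covers physiological observations, so a clinically significant audiogram change could be reported and tabulated, although no audiometric trigger is set. Protocol 8.4 reports no hearing change in the two adult randomised studies when hearing protection was worn. The retreatment audiograms do appear in the schedule reproduced in the SAP; what is missing is an analysis of them. Finally, a loose per-patient cut-off would flag many unaffected patients (Step 6).

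**Conclusion.** The point holds in limited form. 8.J has no per-patient, per-ear criterion, count or listing. Its between-arm test is uninformative about noise common to both coils. It does not cover the retreatment audiograms. For 3 of 50 patients with a 20 dB shift in one ear, the paired test is significant in about 11% to 18% of trials with ears separate, and the active-sham test in about 2% or fewer when both arms are affected. Combining the arms raises detection to about 37% at SD 5 dB, which is still low; the patient table is therefore the more important change.

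These sizes rest on the assumed SD, shift, number affected and ear correlation, none of which the documents give. The three gaps can be read directly from the text and do not depend on those assumptions. Whether only a few patients would be affected is also an assumption. This is a cheap improvement to safety reporting and does not touch the primary analysis.

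**What to change.** In SAP Section 8.J:

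- **(a)** State that left and right ears are summarised separately.
- **(b)** For each ear, tabulate and list patients whose worsening from baseline exceeds a prespecified amount, by arm and for both arms combined, at each phase end. Fix the cut-off before unblinding and in light of test-retest variability. A single 10 dB change at any of 16 readings is likely to be too loose; a larger shift, or one seen at adjacent frequencies, is preferable.
- **(c)** For Phase I, add the within-patient change with both arms combined, and state that a null active-sham difference is not evidence of no noise effect.
- **(d)** Include the audiograms taken before and after each retreatment block, summarised as change across the block and from study baseline.

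The cost is a few sentences and one or two extra tables from data already collected. Some flagged shifts will be test-retest noise and will need comment in the report.
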